Despite current medications, morbidity and mortality of Major Depressive Disorder (MDD) remain high. (Benton, Staab et al. 2007) According to the World Health Organization, MDD affects 121 million people worldwide, and is projected to be the second leading cause of global disability by 2020. Monotherapy with SSRIs is the most widely used treatment for MDD. (Leuchter, Lesser et al. 2008) However, on average, SSRIs require six weeks for onset of action, and two-thirds of those on SSRIs fail to achieve remission.(Trivedi, Rush et al. 2006, Leuchter, Cook et al. 2010) Compounding this problem, patients with residual symptoms are significantly more likely to discontinue treatment or relapse, be hospitalized for medical and psychiatric conditions, or die of suicide and other causes.(Trivedi 2003, Trivedi, Rush et al. 2006, Warden, Trivedi et al. 2007) Although eliminating ineffective treatment trials would significantly reduce patient suffering and healthcare costs, (Taylor, Youngblood et al. 2005, Leuchter, Cook et al. 2010) clinicians currently do not have the tools to objectively select treatment based on an individual's likelihood of remission. Therefore, there is an urgent need to identify markers predictive of an individual's SSRI treatment outcome (Taylor, Youngblood et al. 2005, Leuchter, Cook et al. 2010). Developing this personalized treatment requires increased understanding of the relationship between pretreatment neurobiology, SSRI-induced biological changes, and the corresponding symptom improvements.

Our proposed study, in which FDG-PET scans are acquired before and after escitalopram (or placebo) treatment, avoids these previous limitations by standardizing treatment across all subjects, enrolling 120 subjects to ensure that at least 100 will complete the protocol (largest sample size to date), performing full quantification with arterial blood sampling, and a priori defining the clinical outcome measure as Δ HRDS. Further, we will uncover neurobiological correlates of pathophysiology that span diagnoses.

Potential Noninvasive Estimation: PET research/clinical laboratories have differing levels of software and/or hardware expertise. The key, therefore, to promoting widespread PET use is to develop multiple, validated pathways for noninvasive imaging. In this study, we will evaluate Simultaneous Estimation.

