The PET/MRI procedure will take approximately 1 hour. Before or after the scan, subjects maybe asked to place their leg in the scanner for a quick (<10 min) MRI acquisition. Following the initial PET/MRI, the study treatment visits will be weekly for 4 weeks and then biweekly for 4-8 weeks (4 weeks for placebo subjects and 8 weeks for the escitalopram subjects). However, in the case that patients cannot make an appointment, the study team will accommodate the patients' schedules. The nurse practitioner will be seeing subjects in her office in the Health Sciences Center. In case of emergency, the nurse practitioner will escort the subject to CPEP. The target treatment duration will be 12 weeks, for those on SSRIs. (For this reason, the blind will be broken at week 8.) At each visit, the clinician will complete assessments such as the HDRS and CGI. (Participants who have not attained remission at Week 12, but have HDRS17 \leq 10, will have another optional visit at week 14 to allow a participant close to remission an opportunity to achieve it.) Patients will be randomized to either: 10mg ESC for one week, 20mg for two weeks and 30mg thereafter or placebo. The subjects will be randomized by the pharmacy, keeping the researchers blinded. This may be modified based on clinical judgment. After 8 weeks of treatment, the participant will have another PET/MRI that will follow the same procedures as the first PET/MRI.

For participants using substances (including nicotine, alcohol, prescribed medications, or other medications), we will monitor the times/amounts of substance taken throughout the study by self-report. When possible, substance use will be halted two half-lives before the PET/MRI scan. When that is not possible or will significantly affect the comfort of the subject, baseline and post-treatment PET/MRI scans will be scheduled at similar times relative to substance administration in order to minimize the effects of the substance.

When possible, participants will also have follow-up visits at 6 and 12 months after the start of the treatment period. Subjects in the treatment group will be removed from the protocol and clinically treated if their depression worsens or they respond inadequately to the drug. After the study, subjects in both groups will be given referrals for continuing treatment elsewhere.

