Access to research data will be allowed only to members of the research team or institutional personnel as part of a routine audit. Records may be reviewed by state or federal regulatory agencies and their personnel. Research records, like other medical and clinical records, will be kept confidential to the extent permitted by law. There are legal advocacy organizations that have the authority under state law to access otherwise confidential subject records, though they cannot disclose this information without the subject's consent. All hard copies of records are kept in locked files. Coded computer files will be stored in a database which is password protected and behind an institute and department firewall.

The Data Safety Monitoring Board (DSMB), consisting of the study physician ([name]), psychologist ([name]) and a member external to the study (e.g., [name], Professor of Psychiatry and Director of Clinical Research, Cody Center for Developmental Disabilities) reviews study procedures, subject progress, and imaging data to ensure the safety of participants and the validity and integrity of the data.

Study protocol(s) and consent form(s) were reviewed by the DSMB prior to project initiation. The DSMB also established operating procedures for reviewing patient safety data and source data generated from this study. This includes regular meetings of the DSMB. DSMB recommendations will be shared with the PI (or IRB as necessary) following the meeting. DSMB members will be able to reach each other (or the IRB) in between meetings by phone or e-mail.

IRB protocols and informed consent documents will be reviewed annually by the Stony Brook University IRB. In addition, any serious adverse events (SAE) will be addressed and reported to the IRB and DSMB within 48 hours. An SAE is defined as follows: death, life-threatening adverse event, an unexpected event requiring unplanned inpatient hospitalization, persistent or significant disability/incapacity, and medically significant event.

The PI will also be responsible for reporting any SAEs to the NIMH program officer. Actions taken by the local IRB in response to adverse event reports will be reported to the NIMH Project Officer and the Office of Research Compliance.

Based on its review of the study procedures, subject progress, and imaging data, the DSMB has the authority to prevent the study from starting or to stop the study after it has started.

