Once a patient enrolls in the project, they are given a code number, which is used for all subsequent computer data and/or lab forms. The code list and patient names as well as all data are kept in locked files in locked offices with access limited to those directly responsible for maintenance of these files by the research team. Subjects whose history is obtained through the collection of family history information (from the interviewee) are also considered research subjects. They are subjected to minimal risk because all information is confidential. There are procedures to safeguard confidentiality of the information gathered about them from other family members, including names or identifying information kept on the family history form or in the records. All hard copies of records are kept in locked files. Computer files will be stored in a database which is password protected. The database is stored on a secured server. Only essential staff will be allowed access to this information. The study could not be completed without this information.

Blood samples for genetic testing will be de-identified and coded only with a number; no personally identifying or clinical information will be stored with the samples or provided to testing laboratories.

The physician or nurse practitioner will complete a CGI for all subjects weekly for the first 4 weeks and then weekly or biweekly thereafter. They will be assessed for suicidality or worsening of depression. If this is the case, the subject will be dropped from the study and be treated clinically immediately.

Side effects will be monitored in standard clinical fashion. The physician or nurse practitioner will interview patients about possible side effects at each contact and patients will be encouraged to call with any questions that may arise at any time. Response to side effects will depend on the circumstance. Doses may be titrated or patients may have medication discontinued, if clinically indicated.

References

Benton, T., J. Staab and D. L. Evans (2007). "Medical co-morbidity in depressive disorders." Ann Clin Psychiatry 19(4): 289-303.

Leuchter, A. F., I. A. Cook, S. P. Hamilton, K. L. Narr, A. Toga, A. M. Hunter, K. Faull, J. Whitelegge, A. M. Andrews, J. Loo, B. Way, S. F. Nelson, S. Horvath and B. D. Lebowitz (2010). "Biomarkers to predict antidepressant response." Curr Psychiatry Rep 12(6): 553-562.

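### The SAE definition counts a hospitalization only when the event is unexpected, so a foreseen psychiatric admission can miss the 48-hour report

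*Combined protocol and SAP*

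**What the plan says.** Section G (Data and Safety Monitoring Plan) sets the reporting duty: "any serious adverse events (SAE) will be addressed and reported to the IRB and DSMB within 48 hours". It then defines an SAE by five alternative criteria. Two come first, "death, life-threatening adverse event". The third is hospitalization, worded as "an unexpected event requiring unplanned inpatient hospitalization". The last two are "persistent or significant disability/incapacity, and medically significant event". Reporting to the funder uses the same term: "The PI will also be responsible for reporting any SAEs to the NIMH program officer".

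The documents neither define *unexpected* or *medically significant* nor list expected events.

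Elsewhere the plan foresees deterioration. Section G has subjects assessed for suicidality and worsening when the CGI is completed, and says of those affected: "If this is the case, the subject will be dropped from the study and be treated clinically immediately". Section D (Procedures) also makes worsening a reason for removal in the treatment group. Neither place attaches a reporting step.

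Separately, Section G has the DSMB review subject progress and patient safety data at regular meetings. The interval between meetings is not given.

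**The concern.** Seriousness describes what happened to the subject. Expectedness describes whether it was foreseen. They answer different questions and are normally recorded separately. Here a test of expectedness sits inside one criterion of seriousness.

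The word does a specific job. Elective admissions are already excluded because the hospitalization must be unplanned. All that *unexpected* adds is to take out unplanned admissions that someone judges foreseeable. In a trial of major depression with a washout, a drug-free interval and a placebo arm, an admission for worsening or suicidality is an obvious candidate for that label, and the protocol's own text can be cited in support of it.

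What is at stake is prompt notice. The 48-hour report is the only event report in the plan with a stated clock. An admission that falls outside the definition reaches the IRB and DSMB on no stated timetable. The funder report uses the same definition, so it has the same gap.

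**Working it through.** There is no figure to reproduce and no arithmetic applies. The check reads the definition criterion by criterion.

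**Step 1. Which criteria depend on expectedness?** All five are in Section G.

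| Criterion | Depends on expectedness? |
|---|---|
| Death | No |
| Life-threatening adverse event | No |
| Inpatient hospitalization | Yes, and the admission must also be unplanned |
| Persistent or significant disability or incapacity | No |
| Medically significant event | No, but undefined |

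**Step 2. Can a psychiatric admission be called expected?** The documents do not say so, and nothing rules it out. Worsening is foreseen in Sections D and G, and suicidality in Section G. Section B says that patients with residual symptoms are "significantly more likely to discontinue treatment or relapse, be hospitalized for medical and psychiatric conditions, or die of suicide". That is general background on depression and classifies no trial event, but an investigator could cite it. The Section D sentence "In case of emergency, the nurse practitioner will escort the subject to CPEP" is emergency logistics and adds little either way. Against this, screening (Section C.4) excludes patients at significant risk of suicide and those unlikely to tolerate washout, so an admission could equally be read as unexpected for that subject. Both readings are open.

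**Step 3. Follow an admission for worsening or suicidality through the definition.** Cases B to D are non-fatal and cause no lasting disability.

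| Case | SAE as written? | SAE if *unexpected* is deleted? |
|---|---|---|
| A. Unplanned, judged unexpected | Yes, hospitalization | Yes |
| B. Unplanned, judged expected, life-threatening | Yes, life-threatening | Yes |
| C. Unplanned, judged expected, not life-threatening, judged medically significant | Yes, medically significant | Yes |
| D. Unplanned, judged expected, not life-threatening, not judged medically significant | **No** | **Yes** |
| E. Planned in advance | Not by the hospitalization criterion | Unchanged |

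Only case D changes. Whether an admission falls in C or D depends on an undefined term, so two sites or two clinicians could report the same event differently.

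**Step 4. What happens to case D as written?** It needs no 48-hour report to the IRB or DSMB and no SAE report to the funder. The DSMB could still learn of it when it reviews subject progress and safety data at its next regular meeting.

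**The case against.** The strongest reply is that the other criteria do most of the work. An acute admission for suicidality can readily be called life-threatening or medically significant, and neither criterion asks whether the event was expected. This stands, and it confines the gap to case D. It does not close the gap, because *medically significant* is left to judgment. A reader could also argue that a hospitalization which fails its own specific criterion was not meant to come back in through the general one.

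A second reply is that the label *expected* is an inference, since no text applies it to a psychiatric admission. That is correct. The definition permits non-reporting and does not require it.

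Several stronger readings are tempting, and the documents do not support them:

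- **Such admissions never reach the DSMB, its stopping authority has no data behind it, or a difference between arms could not be seen.** The board reviews subject progress and patient safety data, and its operating procedures are not among the documents. A rule on expedited reporting does not decide what the source data contain.
- **Psychiatric deterioration is the main risk that the protocol names.** The protocol does not rank risks.
- **The criterion was narrowed on purpose.** Nothing in the text shows intent.
- **SAE collection stops when a subject is dropped.** This argues from silence. Section G speaks of any SAE and sets no cutoff at removal.

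**Conclusion.** The concern holds in a limited form. One word in the hospitalization criterion ties seriousness to expectedness. As a result, an unplanned psychiatric admission that is judged expected, is not life-threatening or disabling, and is not judged medically significant carries no 48-hour report and no SAE report to the funder.

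The definition applies to all 120 planned enrollees, but only admissions of that kind are affected. The documents give no psychiatric admission rate and nothing on how investigators would classify such events, so no event count is offered. The conclusion assumes that the definition is applied as worded and that no other document, such as the DSMB operating procedures, overrides it. It depends on no alpha, power or sample-size figure.

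The gap is narrow. It is still worth closing, because it concerns subject safety in a population where the plan itself foresees deterioration, and because closing it costs almost nothing.

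**What to change.** In Section G, delete *unexpected* from the hospitalization criterion, so that any unplanned inpatient hospitalization is an SAE, and say explicitly that psychiatric admissions are included. Record expectedness and relatedness as separate fields on the SAE form, so that this information is kept without deciding whether the event is serious.

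Defining *unexpected* and *medically significant* would be second best, because the hospitalization criterion would still depend on expectedness.

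The cost is a short wording change, two data fields and a few more 48-hour reports. No visit, dose or treatment rule changes, and neither does the status or follow-up of subjects who are dropped.
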